10 STUDY ASSESSMENTS

10.1 Efficacy Assessments

Efficacy will be assessed by disease recurrence and OS. To assess disease recurrence, CT/MRI scans, cystoscopy (for subjects with a bladder), and urine cytology will be performed. Assessments are scheduled based on first dosing day of the dosing cycle and do not change due to dose interruptions and will be conducted as detailed in [Table 2](#) and [Table 3](#).

Chest, abdomen, and pelvic CT scans are required for all subjects at screening, unless available within 28 days before randomization. A contrast-enhanced MRI (if possible) of the chest, abdomen, and pelvis should be performed if a subject is known to have a contraindication to IV contrast at baseline or develops a contraindication during the trial. (Note that for individual subjects, the same modality [CT or MRI] should be used for radiographic assessments throughout the study). Details are provided in the Subject Scanning Guide. Scans must be sent for BICR to confirm absence of residual or metastatic disease prior to randomization. All postbaseline radiological assessments, including imaging obtained at unscheduled time points to determine disease recurrence, as well as imaging obtained for other reasons but captures radiologic recurrence, will be sent for BICR. Subject's imaging will be read locally and submitted for BICR as well as any supporting report (including pathology and cytology reports) if a biopsy was conducted at the time when recurrence was suspected. At the time of investigator-determined disease recurrence, a confirmatory BICR assessment should be requested. Refer to the Study Manual for details regarding image collection and transfer or shipment.

Subjects should remain on study treatment until local/regional or contralateral invasive or metastatic recurrence is confirmed by BICR. If BICR confirms recurrence (local/regional or contralateral invasive or metastatic recurrence, whichever occurs first), the subject must be permanently discontinued from study treatment. If locally diagnosed local/regional or contralateral invasive or metastatic recurrence is not confirmed by BICR, treatment continuation is allowed at Investigator's decision. BICR diagnosis of a local/regional or contralateral invasive or metastatic recurrence, independently from and undiagnosed by local team, will not be communicated to the clinical site (see Section [8.1.1](#)).

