Acceptable criteria for the diagnosis of recurrence are listed in [Table 8](#) under “Unequivocal Recurrence”. For some recurrence sites, both histologic/cytologic and radiologic criteria for unequivocal recurrence are described. Histologic/cytologic confirmation is the preferred criteria to determine unequivocal recurrence, and new lesions should be biopsied to confirm recurrence when safe and feasible. Radiologic assessments completed to evaluate for disease recurrence must be submitted for BICR. Refer to the Study Manual for details regarding image collection and submission. New lesions meeting criteria for radiologic unequivocal recurrence, as well as highly suspicious lesions, should be biopsied to confirm recurrence when appropriate. Biopsy reports, including pathology and cytology reports, must be submitted for BICR (as well as radiological imaging as described above). Refer to the Study Manual for details regarding report collection and submission. For highly suspicious lesions or indeterminate lesions that are not amenable to biopsy, interval imaging surveillance should be performed as clinically indicated until disease recurrence is confirmed by biopsy or the subject has radiographic evidence of unequivocal recurrence according to [Table 8](#). The frequency of surveillance imaging should be determined by the rate of tumor growth. For indeterminate or highly suspicious lesions that are followed using interval imaging surveillance, if recurrence is confirmed, the date of recurrence will be the *date of first recognition of the findings*. When both imaging and biopsy dates are available, the earlier date should be used as the date of recurrence.

Table 8: Definitions of Recurrence by Site

Site of Recurrence	Unequivocal Recurrence	Highly Suspicious Lesions	Indeterminate Lesions
Renal bed	Pathologic confirmation of disease (cytology or histology) OR Radiologic evidence of new focal defects on CT or MRI imaging that is consistent with recurrence or new tumor per RECIST v1.1, ie, its longest diameter is ≥ 1 cm.		
Ureteric bed	Pathologic confirmation of disease (cytology or histology) OR		

Site of Recurrence	Unequivocal Recurrence	Highly Suspicious Lesions	Indeterminate Lesions
	Radiologic evidence of new focal defects on CT or MRI imaging consistent with recurrence or new tumor per RECIST v1.1.		
Invasive Urinary Bladder Cancer (UBC):	Cystoscopic and TUR/biopsy confirmation of new lesions, stage T2, T3, or T4.		

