Nonmuscle Invasive Bladder Cancer (NMIBC)	Cystoscopic and TUR/biopsy confirmation of new lesions, stage Ta, Tis, or T1.		
Upper Tract Urothelial Carcinoma (UTUC)	Histologically/cytologically confirmed high grade, invasive UTUC defined as pT1, T2, T3, and T4 OR Histologically/cytologically confirmed high grade noninvasive or low-grade noninvasive UTUC defined as pTa and pTis		
Lung and pleura	Pathologic confirmation of disease (cytology or histology) OR >3 non-calcified pulmonary nodules, all >1 cm or new innumerable nodules of any size; for solitary pulmonary nodules, >2 cm. Proof of neoplastic pleural effusion must be established by cytology or pleural biopsy.	Any number of nodules associated with thoracic adenopathy or not present at baseline	Any pulmonary nodules not meeting criteria for unequivocal recurrence or highly suspicious lesion
Liver	Pathologic confirmation of disease (cytology or histology) OR Abdominal CT or MRI demonstrating lesion ≥ 1 cm with confirmation of growth ≥ 5 mm or appearance of ≥ 1 new lesions on subsequent scans ≥ 4 weeks later. Proof of neoplastic abdominal ascites must be established by cytology or histology.	Nodules <10 mm in size that do not appear compatible with benign processes; lesions of any size not present on prior imaging	Any mass not meeting criteria for other 2 categories or that characteristically enhances compatible with benign processes
Central nervous system	Positive cerebral spinal fluid (CSF) cytology or biopsy OR Positive brain CT imaging or MRI imaging consistent with metastatic disease.		
Lymph Node	Pathologic confirmation of disease (cytology or histology) OR Lymph nodes ≥ 1.5 cm short axis, with confirmation of growth ≥ 5 mm or appearance of new lesions on subsequent scans ≥ 4 weeks later	Lymph nodes <1.5 cm short axis that increase in size on subsequent imaging but remain less than 1.5 cm	Lymph nodes that are stable ≥ 1 cm and <1.5 cm short axis

Site of Recurrence	Unequivocal Recurrence	Highly Suspicious Lesions	Indeterminate Lesions
Bone	Pathologic confirmation of disease (cytology or histology) OR ≥2 lesions of the bone on bone scan confirmed on CT or MRI. For solitary lesions, subsequent scan required to demonstrate growth or ≥ 1 new lesion ≥4 weeks apart	≥1 bone lesion with characteristic findings on imaging	Any bone lesion without characteristic findings or not meeting criteria for unequivocal recurrence or highly suspicious lesion

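### On imaging alone, Table 8 makes one lung nodule over 2 cm a primary DFS event, but two or three nodules of any size, growing or not, are no event

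*Protocol*

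**What the plan says.** Protocol Section 11.3.3 takes the recurrence criteria for primary DFS from Section 10.1. There, "Acceptable criteria for the diagnosis of recurrence are listed in" Table 8, in the column for unequivocal recurrence. The other two columns, highly suspicious and indeterminate, are not events.

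The lung row accepts pathology or, on imaging, more than three "non-calcified pulmonary nodules, all >1 cm or new innumerable nodules of any size; for solitary pulmonary nodules, >2 cm". Its highly suspicious column takes "Any number of nodules associated with thoracic adenopathy or not present at baseline", and its indeterminate column takes "Any pulmonary nodules not meeting criteria for unequivocal recurrence or highly suspicious lesion".

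Section 10.1 prefers histology or cytology and asks for biopsy where it can be done safely. For lesions that cannot be biopsied, "interval imaging surveillance should be performed as clinically indicated until disease recurrence is confirmed by biopsy or the subject has radiographic evidence of unequivocal recurrence" as Table 8 defines it. If recurrence is confirmed later, its date goes back to when the findings were first recognised.

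A living subject without a bladder and without centrally confirmed recurrence is censored at the last radiology assessment (Protocol Section 11.3.3). For a subject with a bladder, the same applies if a cystoscopy within 6 months was negative for muscle-invasive disease. Otherwise censoring is at the last complete recurrence assessment. SAP Section 6 applies the cystoscopy-conditional rule to all subjects.

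**The concern.** A recurrence definition should be monotone: adding disease to a subject who already meets it should not take the subject out of it. The lung row breaks this. A second or third nodule moves a subject from event to highly suspicious, and no later enlargement of those nodules brings the subject back.

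The rule feeds the primary endpoint directly. Table 2 (footnote p) also has sites read scans locally against Table 8, so investigator-reviewed DFS and MFS are exposed too. An affected subject is credited with disease-free time while probable metastases are visible. The censoring that follows is then related to the outcome and not independent of it.

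**Working it through.** **1. The plan's own figure.** Inputs from Protocol Section 11.2: HR 0.5, one-sided alpha 0.025, power 80%, 1:1 allocation. The Freedman formula gives

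d = ((1 + HR)/(1 − HR))² × (z₀.₉₇₅ + z₀.₈₀)² = 9 × (1.960 + 0.842)² = 70.6, or 71 events.

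Power at 70 events is Φ(√70 × 0.5/1.5 − 1.960) = Φ(0.829) = 79.6%. The stated 70 events and 80% power are reproduced. (The Schoenfeld formula gives 66 events, and 82.6% power at 70.)

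**2. The lung rule applied as written (imaging only, countable nodules).** A set qualifies if there is one nodule and it is >2 cm, or if there are more than three and all are >1 cm. New innumerable nodules qualify separately. The sizes below are illustrations.

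| Nodules (cm) | Summed diameter | Event on imaging? |
|---|---|---|
| 2.1 | 2.1 | Yes |
| 1.9 | 1.9 | No |
| 3, 3 | 6 | No |
| 5, 5 | 10 | No |
| 5, 5, 5 | 15 | No |
| 1.1, 1.1, 1.1, 1.1 | 4.4 | Yes |
| 1.1, 1.1, 1.1, 1.0 | 4.3 | No |
| 5, 5, 5, 0.9 | 15.9 | No |

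The last two rows fail even if the size condition is read as asking only for more than three nodules above 1 cm, because each has only three.

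**3. Growth routes in Table 8, side by side.**

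- Liver and other organs: a lesion ≥1 cm with growth ≥5 mm, or a new lesion, at least 4 weeks later.
- Lymph node: short axis ≥1.5 cm with growth ≥5 mm, or new lesions, at least 4 weeks later.
- Solitary bone lesion: growth, or a new lesion, at least 4 weeks apart.
- Lung: none.

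Surveillance of two or three enlarging lung nodules therefore has no radiologic end point of its own. The subject becomes an event only through pathology, a rise in nodule number that meets the rule, recurrence elsewhere, or death.

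**4. Size.** The documents do not give the share of recurrences that present as two or three unbiopsied lung nodules, so the loss cannot be computed. As an assumption, let a fraction f of true events go unrecorded. True events needed to record 70 are 70/(1 − f). If the analysis were instead held to a fixed date, 70(1 − f) would be recorded, and power follows from step 1.

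| f | True events needed | Recorded at fixed date | Power at fixed date |
|---|---|---|---|
| 2% | 71.4 | 68.6 | 78.8% |
| 5% | 73.7 | 66.5 | 77.6% |
| 10% | 77.8 | 63.0 | 75.4% |

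The planned analysis was event-driven, so the middle columns matter less than the first: missed events would mainly have postponed it.

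**The case against.** The strongest reply is that the gap is narrow. Pathology is open for any number of nodules and is the preferred route. New nodules of any number are highly suspicious, and Section 10.1 asks for biopsy of such lesions where appropriate. A subject is lost only if biopsy is never feasible or diagnostic, no qualifying nodules appear, no other site recurs and the subject does not die. That stands: such subjects can fail to become events, but not all will. Central review is blinded in both arms, and nothing shows a difference between arms. Any central-review charter and the Study Manual are not among the documents and might hold a further reading rule.

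The wording might also be read more kindly. If solitary meant each discrete nodule, two or three nodules above 2 cm would qualify, and the gap would shrink to those of 2 cm or less. If more than three was meant as three or more, two nodules would still be uncovered. The text does not clearly support either reading.

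Three stronger inferences are tempting, and the documents do not bear them out:

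- **Event dates run late by a scan interval.** Section 10.1 back-dates confirmed recurrences, and it sets surveillance of these lesions by clinical need and rate of growth, not by the fixed scan schedule.
- **Affected subjects must stay on study drug.** Section 10.1 says "Subjects should remain on study treatment until local/regional or contralateral invasive or metastatic recurrence is confirmed by BICR". But that section and Section 8.1.1 also leave continuation to the investigator when central review does not confirm a local diagnosis.
- **The bone row has the same defect.** It asks for at least two "lesions of the bone on bone scan confirmed on CT or MRI", and Table 2 schedules no bone scan. Yet the row covers every lesion count, and Section 10.1 provides for unscheduled imaging to establish recurrence.

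**Conclusion.** The lung row is wrong as written. On imaging alone it ranks two or three nodules of any size, and four or more countable nodules with one at or below 1 cm, below a single nodule just over 2 cm, and it offers no growth route. For five or more nodules with at least four above 1 cm, the exclusion rests on the literal force of the requirement that all exceed 1 cm. The finding about two or three nodules rests on solitary meaning exactly one.

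The harm is confined to events never confirmed, or still unconfirmed at data cutoff. A reader may want a count of lost events, but the documents give no site distribution. The figure of about 71 to 78 true events per 70 recorded only illustrates an assumed 2% to 10% loss.

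SAP Sections 1, 5 and 8.1 record early termination, no interim analysis, no hypothesis test and Kaplan-Meier description only. The present effect is therefore on event classification in descriptive DFS and MFS, not on a test result.

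**What to change.** Reword the lung row of Table 8, and align any central-review charter, so that the radiologic criterion is monotone in disease burden:

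- The existing >2 cm criterion applies to any qualifying nodule, however many others are present.
- Additional smaller nodules never disqualify a set that otherwise qualifies.
- Two or three nodules that do not qualify on size have a confirmation route by growth or a new lesion on a later scan, with a minimum size, parallel to the liver and other-organ rows. By the second rule, a further small nodule does not close this route.

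The sponsor's imaging experts should set the exact thresholds. Centrally confirmed recurrence also triggers discontinuation of study drug, so the new wording must be reconciled with Protocol Sections 8.1.1 and 10.1.

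The cost is wording in one table row and the charter, with no added scheduled scan or reader. The downside is that a few benign nodules could be called recurrence, which the size and growth conditions limit.

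For the terminated study, check whether a charter already closes the gap. Identify in the clinical study report any subjects with two or three unbiopsied lung nodules, with how each was classified and censored.

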10.2 Pharmacokinetic Assessments

Blood samples will be collected at the time points specified in [Table 3](#). All blood samples will be taken from a central line, by direct venipuncture, or with an indwelling cannula inserted in a peripheral vein.

On the days of PK sampling, subjects should take their study drug at the clinic after the predose PK sample is taken. Subjects who forget and take their study drug at home will be excluded from PK analysis for that day and should not have blood samples collected for PK analysis. If a subject is not on study medication, then no PK will be collected. PK sampling will resume once the subject is back on study medication.

Complete dosing information, including the date and time of actual blood draw and time of the last study drug dose before the sampling, should be obtained on all sampling days and recorded on the appropriate blood collection eCRF. If any of the scheduled sampling times are missed or a sample is not drawn according to schedule, the actual collection date and time should be recorded, and the remaining samples should be collected on schedule whenever possible.

Refer to the Laboratory Manual for complete instructions on PK sample collection, processing, handling, storage and shipment.

Plasma concentrations of infigratinib and its active metabolites (BHS697, BQR917, and CQM157) will be measured by a central laboratory using a validated liquid chromatography-tandem mass spectrometry (LC-MS/MS) assay with a lower limit of quantification (LLOQ) of approximately 1.0 ng/mL. Concentrations below the LLOQ will be reported as below the quantification limit, and missing samples will be labeled accordingly.

PK parameters listed in [Table 9](#) will be estimated for infiratinib and its active metabolites. Concentrations of metabolites will be reported and summary statistics (eg, mean, standard deviation, %CV) calculated, as appropriate.

Table 9: Pharmacokinetic Parameters

Term	Definition
C _{trough}	Trough observed plasma concentration (before drug administration)
C _{max}	Maximum observed plasma concentration after drug administration (defined as the 4-hour postdose concentration)

10.3 Assessment of Biomarkers and Eligible FGFR3 Alterations

Biomarker assessments will be performed to confirm subject eligibility and potentially aid in understanding the effects of infiratinib treatment on biomarkers of urothelial carcinoma and FGFR pathway regulation as related to clinical outcome.

Subjects must have written documentation of the FGFR3 alteration by F1CDx testing (through Foundation Medicine USA). The sponsor must review all written documentation of the FGFR3 alteration by F1CDx that was obtained as part of routine clinical care for adherence to the study protocol.

If F1CDx testing is not performed as part of routine clinical care, molecular prescreening is required to confirm the presence of FGFR3 alteration from tissue (subjects must provide written informed consent for the molecular prescreening). See Appendix 5 (Section [17.5](#)) for details on the specimen requirements for F1CDx testing. F1CDx should be performed using the tumor sample from the definitive surgical resection (cystectomy, nephroureterectomy, or distal ureterectomy) because this tumor provides the most current readout of FGFR3 status. If the surgical specimen is not available, an archival biopsy sample can be used when prespecified criteria are met (see Section [9.1](#)). The sponsor must review all cases where an archival biopsy sample is used to assess FGFR3 alterations (either locally as part of routine clinical care or centrally through molecular prescreening) for adherence to the study protocol. Molecular prescreening results (and any leftover tumor material) will be used to validate F1CDx as a companion diagnostic for the identification of patients with urothelial carcinoma who may benefit from treatment with infiratinib following the detection of FGFR3 alterations. The companion diagnostic validation may require a bridging study that will use leftover tumor samples from enrolled subjects collected during prescreening.

Subjects with an FGFR3 alteration identified as described below (in addition to all other inclusion/exclusion criteria) will be eligible for enrollment in the study. Subjects with susceptible FGFR alteration(s) other than the ones described below will be enrolled in the study only **following discussion between the investigator and the medical monitor.**

- **FGFR3 mutation** is confirmed if:
 - FGFR3 gene is mutated in Exon 7 (R248C, S249C), Exon 10 (G370C, A391E, Y373C), or Exon 15 (K650M/T, K650E/Q).

- **FGFR3 gene fusion/rearrangement** is confirmed based on the following criteria:
 - Any fusion/rearrangement with a literature-derived known partner gene regardless of strand or frame.
 - Fusion/rearrangements in the same strand that are in frame with a novel partner gene.
 - Fusion/rearrangements with one breakpoint in the intron 17 - exon 18 hotspot region and the other breakpoint in an intergenic region or another gene. This rule excludes 3' duplications comprising only exon 18.
- The amino acid numbers for the FGFR3 mutations refer to the functional FGFR3 isoform 1 (NP_000133.1) that is the NCBI Refseq ID used to report genetic alterations in FGFR3 by the F1CDx test.

Assessment of the PD-L1 status is not an eligibility criterion, subjects are allowed to participate in the study regardless of the PD-L1 status results. Nevertheless, PD-L1 results are required and will be recorded in the eCRF. If PD-L1 status is not already known, the assessment will be initiated on subject's tumor sample from the definitive surgery or a biopsy (following the same rules for biopsy sample as described for the FGFR3 testing requirements in Section 9.1; refer to the Laboratory Manual for additional information). If PD-L1 status was not available at screening, the PD-L1 testing can be initiated at C1D1 or at any time after the subject is deemed eligible.

If PD-L1 status is not already known at the time of screening, tumor tissue collected prior to treatment with study drug will be assessed for PD-L1 protein expression using a Food and Drug Administration (FDA)-approved immunohistochemistry (IHC) assay (PD-L1 IHC 22C3 pharmDx) to support the exploratory objectives. If not already known, the PD-L1 IHC should be performed using the tumor sample from the definitive surgical resection (cystectomy, nephroureterectomy, or distal ureterectomy). If the surgical specimen is not available, a biopsy sample can be used instead. Refer to the Laboratory Manual for additional details regarding PD-L1 biomarker assessments. If tumor tissues or biopsy sample are not available, PD-L1 testing will not be expected.

Blood and urine samples for assessment of cfDNA will be collected as outlined in [Table 2](#) and [Table 3](#) to support exploratory objectives. These samples will be used for analysis of DNA to explore whether genetic alterations or other biomarkers found in tumor samples may also be observed in blood or urine, and if any biomarkers are prognostic or predictive of efficacy, disease recurrence, and/or resistance to study medications.

With subject consent, tumor samples collected upon local/regional or contralateral invasive or metastatic recurrence as part of standard of care may be provided to the sponsor for exploratory objectives related to biomarkers of urothelial carcinoma biology and the potential association of biomarkers with efficacy, disease recurrence, and resistance to study medications. Additional archival tumor samples (including leftover DNA from subjects who underwent molecular prescreening) may also be collected for biomarker assessments to support the exploratory objectives. Biomarker assessments using tumor tissue left over from FGFR3 prescreening and cfDNA derived from blood or urine may include (but are not limited to): (1) genetic analysis

including transcriptomic, whole genome sequencing, whole exome sequencing, or targeted gene sequencing; (2) protein analysis including proteome analysis and IHC.

QED designated laboratories(s) will be used for processing of all tumor, blood samples, and urine samples collected. The central laboratory will provide kits to collect and ship these samples to QED designated lab(s) for analysis. Refer to the Study Manual for additional instructions on the handling, storage and shipment of samples. Sample collection must be captured on the appropriate eCRF and requisition page(s).

If the subject consents to long-term storage, samples collected during molecular prescreening or as part of the main study may be stored for up to 15 years for additional future research related to infigratinib, cancer, or other study treatments. This may also include research to help develop ways to detect, monitor, or treat cancer. A decision to perform additional research studies would be based on outcome data or from new scientific findings related to the drug class or disease, as well as reagent and assay availability.

